6.2 Baseline Characterization

The baseline characteristics summarized for participants randomized within RGC are the same as specified in the M-SAP with the addition of ALSAQ-40 domain scores and SI, CNS-BFS total score, King's stage, weight, body mass index (BMI), serum urate concentration, serum creatinine concentration, serum NfL concentration, urinary p75[ECD], and vital capacity predicted from quantitative voice characteristics.

6.3 Primary Efficacy Analysis and Supportive Analyses

The primary analysis for RGC is a Bayesian shared-parameter, repeated-measures model of ALSFRS-R that accounts for loss of follow-up due to mortality. Details of the model, including documentation of operating characteristics under a range of scenarios, are provided in the "ALS Master Protocol Recommended Statistical Analysis, Design and Simulation Report" (Appendix 1 to the Master Protocol). The Bayesian shared-parameter, repeated-measures model will be

applied to the FAS analysis set as the primary analysis, to the ECM and ERO analysis sets as sensitivity analyses, and to the EPP analysis set as a supportive analysis.

The estimand of the primary analysis is the relative rate of disease progression (the "disease rate ratio" or DRR) of the two active treatment groups relative to placebo in the FAS population under an assumption that active treatment slows mean time to death or death equivalent by the same proportion as treatment slows the mean rate of functional progression as measured by change in ALSFRS-R total score over time. The estimand is defined by the following attributes:

- Treatment: CNM-Au8 administered orally at dosages of 30 mg/d and 60 mg/d vs. placebo.
- Population: FAS population as defined in Section 6.1.
- Variables: time to death or death equivalent and rate of change in ALSFRS-R total score from baseline to the Week 24 Visit.
- Intercurrent event 1: treatment discontinuation due to death: no ALSFRS-R data from participants who reach the death or death equivalent endpoint are included in the analysis; instead, death or death equivalent are handled by a mortality component within the model, composite variable strategy approach.
- Intercurrent event 2: treatment discontinuation not due to death: handled via treatment policy approach, all data will be used including data collected during the placebo-controlled period after treatment discontinuation regardless of concomitant medication, for those participants who have not been censored due to mortality. Missing data post-treatment will not be imputed, handled via missing at random assumption.
- Population-level summary: mean ratio of hazard or progression rate of active treatment relative to placebo.

6.4 Interim Analysis

RGC will be considered for early stopping for futility according to the interim analysis schedule and definition specified in the "ALS Master Protocol Recommended Statistical Analysis, Design and Simulation Report" (Appendix 1 to the Master Protocol). RGC will not be stopped early for success.

6.5 Secondary Efficacy Analyses

6.5.1 Hierarchical Testing

Primary inference for secondary efficacy endpoints will be based on analysis of the FAS analysis set using a joint-rank comparison for the combined assessment of function and survival (CAFS (Section 6.5.2 below), a repeated-measures linear mixed model for SVC (see Section 6.5.3 below), and Kaplan-Meier product-limit estimates and log-rank test for the primary survival endpoint (see Section 6.5.4 below) with a comparison between all active arm participants (i.e., the average of both 30 mg/d and 60 mg/d dosage groups) vs. placebo participants. The sequence for testing secondary efficacy endpoints is the following:

1. CAFS,
2. SVC,
3. Survival.

If the primary analysis indicates a significant slowing in disease progression from the Bayesian shared-parameter, repeated-measures model of ALSFRS-R and mortality, then each secondary efficacy endpoint in succession would be declared significant in the specified sequence using a comparison-wise criterion of two-tailed $p < 0.05$. After the first failure to declare significance, no endpoints lower in the hierarchy can be significant. This sequential closed-testing procedure controls the overall type 1 error rate at 5%. Nominal comparison-wise p-values for secondary efficacy endpoints will also be reported.

6.5.2 CAFS

The test consists of calculating a rank-sum score for each individual relative to pair-wise comparisons with all other participants. Participants are first ranked according to time to death or death equivalent when that is observed for both members of a pair or when one is censored after the observed event time for the other. Pairs that cannot be ranked by time to death or death equivalent are subsequently ranked by absolute change from baseline in ALSFRS-R total score at the maximum follow-up time at which both participants have an observation.

The primary CAFS analysis is the same as specified in the MPRDR with the clarification that the active treatment group pools participants randomized to 30 mg/d CNM-Au8 and 60 mg/d CNM-Au8.

The estimand is the stochastic probability that a randomly selected active participant will rank higher than a randomly selected placebo participant based on time to death or death equivalent or change from baseline in ALSFRS-R. The estimand is defined by the following attributes:

- Treatment: CNM-Au8 administered orally at dosages of 30 mg/d and 60 mg/d vs. placebo.
- Population: FAS population as defined in Section 6.1.
- Variables: ranksum for relative time to death or death equivalent up to the Week 24 Visit or absolute change from baseline in ALSFRS-R total score.
- Intercurrent event: treatment discontinuation: handled via treatment policy approach, with pair ranked comparisons up at the maximum follow-up time at which both participants have an observation.
- Population-level summary: difference in means of ranks of active treatment relative to placebo.

Inference from this analysis is supportive of inference from the Bayesian shared-parameter, repeated-measures model for the primary endpoint and is the primary analysis for this secondary endpoint.

The following SAS code specifies the analysis:

```
proc mixed data=work.cafs;  
  class trtrnd(ref='0');  
  model Rank = sx2b1 dFRS rlz edv trtrnd / solution clparm;  
  estimate "Active vs. Placebo (one-sided)" Treat 1 -1 / cl upper;  
run;
```

where trtrnd indicates treatment group (active = 1 or placebo = 0), Rank is the sum of the ranks (-1, 0, 1) of each participant vs. every other participant in the FAS analysis set, sx2b1 is years

since ALS symptom onset, dFRS is pre-baseline slope, r1z is an indicator of riluzole use at baseline, and edv is an indicator of edaravone use at baseline. A significant difference requires interpretation based on estimates from the survival analysis described in Section 6.5.4 and the repeated-measures analysis of ALSFRS-R total score described in Section 6.5.3.

In addition to the joint-rank CAFS analysis of PAV-free survival and change in ALSFRS-R total score including adjustment for covariates, the following additional joint-rank analyses will also be performed:

1. SVC will be analyzed as a joint-rank test by substituting the change from baseline of SVC in place of ALSFRS-R total score as an additional supportive analysis,
2. An additional set of joint-rank analyses will use multiple imputation to extend follow-up of (i) ALSFRS-R total score and (ii) SVC for participants who early terminate, withdraw consent, or are lost to follow-up as supportive analyses,
3. An additional set of joint-rank analyses for (i) ALSFRS-R total score and (ii) SVC will use time to death independent of any death equivalent as supportive analyses,
4. An additional set of joint-rank analyses for (i) ALSFRS-R total score and (ii) SVC will adjust rank scores in a linear model with the following covariates: time from ALS symptom onset, delta-FRS, baseline use of riluzole, baseline use of edaravone, and baseline serum NfL level, and
5. An additional set of joint-rank analyses for (i) ALSFRS-R total score and (ii) SVC without adjustment and comparing pairs of participants at the last jointly observed time point as sensitivity analyses.

The multiple imputation model referenced as method 2 above and used to extend follow-up of functional scores for participants who early terminate, withdraw consent, or are lost to follow-up will use linear regression with covariates of time since symptom onset, delta-FRS, baseline riluzole use, baseline edaravone use, and each observed functional score prior to a missing assessment.

Inference from the joint-rank analyses of SVC are supportive of inference from the repeated-measures model. Primary inference from the joint-rank CAFS analyses will compare survival by time to death or death equivalent, will compare change in function to the last jointly observed time point, and will adjust for the specified covariates.

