This Regimen-specific Statistical Analysis Plan (R-SAP) for the CNM-Au8 regimen (RGC) specifies any modification from the default outcome measures, analysis samples, and planned analyses for the placebo-controlled period of the HEALEY ALS Platform Trial as specified in the Master SAP (M-SAP). The M-SAP and this R-SAP supplement the Master Protocol, the "ALS Master Protocol Recommended Statistical Analysis, Design and Simulation Report" (Appendix 1 to the Master Protocol), and the RGC Regimen-specific Appendix (RGC RSA). Please refer to the Master Protocol and the RGC RSA for details on the rationale for the study design, eligibility criteria, conduct of the trial, clinical assessments and schedule of assessments, definitions and reporting of adverse events, data management conventions, and regulatory oversight and compliance procedures. The "ALS Master Protocol Recommended Statistical Analysis, Design and Simulation Report" (MPRDR) and any regimen-specific deviations described in the RGC RSA, and this R-SAP are authoritative in defining the primary and interim analyses. In case of discrepancies between the RGC RSA and this R-SAP concerning use of shared placebos, this R-SAP is authoritative. In case of discrepancies between either SAP and the Master Protocol and the RGC RSA concerning matters of analysis other than the primary and interim analyses and use of shared placebos, the M-SAP and this R-SAP are authoritative. In case of discrepancies between the M-SAP and this R-SAP, this R-SAP is authoritative. On all matters not related to analysis, the Master Protocol and the RGC RSA are authoritative. The following table describes relationships among the relevant documents in adjudicating possible discrepancies with higher numbers indicating greater authority.

Issues potentially requiring adjudication	Master Protocol	RGC RSA	MPRDR	M-SAP	RGC R-SAP
Use of shared placebos	1	4	2	3	5
Primary and interim analysis specifications not related to use of shared placebo	1	5	4	2	3
Statistical analysis specifications not related to use of shared placebo or primary and interim analyses	1	3	2	4	5
All matters not related to statistical analysis	4	5	1	2	3

2. Study Design

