- Population: FAS population as defined in Section 6.1.
- Variables: absolute change in endpoint from baseline to the Week 24 Visit.
- Intercurrent event: treatment discontinuation: handled via treatment policy approach, all data will be used including data collected during the placebo-controlled period after treatment discontinuation. Missing data post-treatment, including data missing due to death, will not be imputed, handled via missing at random assumption.

- Population-level summary: difference in conditional means of active treatment relative to placebo.

Inference from this analysis is supportive of inference from the Bayesian shared-parameter, repeated-measures model for the primary endpoint and is the primary analysis for the secondary SVC endpoint.

The following SAS code specifies the linear contrast for an endpoint measured every 8 weeks and assuming that the sort order for treatment group is placebo, 30 mg/d CNM-Au8, and 60 mg/d CNM-Au8 and visits are sorted chronologically:

```
estimate "3|Act vs Plb|dWk 24"
          post*trtrnd*visit 2 0 0 -2 -1 0 0 1 -1 0 0 1 / cl divisor=2;
```

A significant difference in 24-week change in the direction of improved function would support inference that CNM-Au8 treatment reduced progression over 24 weeks for the efficacy endpoint being tested.

A separate supportive analysis for clinical endpoints (ALSFRS-R total and domain scores, HHD upper extremity, lower extremity, and global average percentages, SVC, FVC by home spirometry, ALSAQ-40 domain scores and SI, and CNS-BFS total score) will include centered baseline serum NfL level and the interaction of centered baseline serum NfL level and visit as additional covariates.

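### The CAFS code specifies a one-sided contrast on an effect missing from its model, while SAP 6.5.1 tests CAFS, the first key secondary gate, at two-tailed 0.05

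*SAP*

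**What the plan says.** SAP 6.5.1 sets a fixed sequence of CAFS, SVC and survival, entered only if the Bayesian primary analysis succeeds. Each endpoint is declared significant "using a comparison-wise criterion of two-tailed $p < 0.05", and the first failure closes everything below it. The section states an overall type 1 error of 5% for the sequence.

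SAP 6.5.2 describes the CAFS joint-rank test as the primary analysis for that endpoint and introduces its program with "The following SAS code specifies the analysis". The model line is "model Rank = sx2b1 dFRS rlz edv trtrnd / solution clparm", the only CLASS variable is trtrnd, and the text below the code defines trtrnd as 1 for active and 0 for placebo. The only contrast is "estimate 'Active vs. Placebo (one-sided)' Treat 1 -1 / cl upper". The section closes by saying that primary inference from the joint-rank CAFS analyses "will compare change in function to the last jointly observed time point, and will adjust for the specified covariates", so the covariate-adjusted program is the one that feeds the hierarchy.

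**The concern.** The contrast conflicts with the rest of the SAP in two ways. It names an effect that its own model does not contain. It also asks for one tail where 6.5.1 requires two. Correcting the name alone leaves the second conflict: the program then returns an upper-tail p-value from the contrast and a two-tailed p-value for trtrnd from the solution table. Nothing in 6.5.1 or 6.5.2 says which line of output is decisive, or that the upper-tail value should be doubled or compared with 0.025.

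CAFS gates SVC and survival, so a borderline result would leave three key secondary claims open to argument about which p-value counts. That choice should be closed before the data are seen.

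**Working it through.** **1. Does the contrast match the model?** Effects in the model: sx2b1, dFRS, rlz, edv, trtrnd. Effect in the contrast: Treat. It is not in the list, and the SAP does not define it.

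**2. Which tail favours active?** The CAFS estimand in 6.5.2 is the probability that an active participant ranks higher than a placebo participant. The upper tail of active minus placebo is therefore the benefit direction.

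**3. The plan's own figure.** In a fixed sequence with no effect on any endpoint, the chance of any rejection equals the chance of rejecting at the first step. With two-tailed 0.05 this is 2 × (1 − Φ(1.960)) = 0.050. The stated 5% reproduces. Simulation with one million draws and between-endpoint correlations of 0, 0.5 and 0.8 gave 0.0498 to 0.0500.

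**4. The coded p-value read against 0.05.**

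| | Two-tailed, as in 6.5.1 | One-sided p against 0.05 |
|---|---|---|
| Critical z for benefit | 1.960 | 1.645 |
| Benefit-direction error of the CAFS test | 2.5% | 5.0% |
| Total size of the CAFS test | 5% | 5% |
| z = 1.80 | p = 0.072, fails | p = 0.036, passes |

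**5. How often the two readings differ.** They differ for benefit when z lies between 1.645 and 1.960.
- No CAFS effect: Φ(1.960) − Φ(1.645) = 0.975 − 0.950 = 0.025.
- Worst case over any true effect: mean z at the midpoint, (1.645 + 1.960)/2 = 1.80; half-width (1.960 − 1.645)/2 = 0.158; 2Φ(0.158) − 1 = 0.125.

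**6. Power, for illustration.** The documents give no CAFS power. Assuming 80% two-tailed, the mean of z is 1.960 + 0.842 = 2.802, and Φ(2.802 − 1.645) = 0.876.

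**7. Including the primary gate.** The supplied documents give neither the one-sided error level of the primary analysis (a) nor its correlation with CAFS (ρ), so both are assumed. With no effect on either, the chance of a false CAFS benefit claim is P(Z₁ > z₁₋ₐ and Z₂ > c), with Z₁ and Z₂ bivariate normal:

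| a | ρ | c = 1.960 | c = 1.645 |
|---|---|---|---|
| 0.01 | 0 | 0.025% | 0.05% |
| 0.025 | 0.7 | 0.83% | 1.23% |
| 0.05 | 0.9 | 2.0% | 3.2% |

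Across this range the chance stays below 5%.

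**8. Does anything else in the SAP settle it?** The table in section 1 ranks documents for "Statistical analysis specifications not related to use of shared placebo or primary and interim analyses": the R-SAP scores 5 and the MPRDR 2. Both conflicting statements are in the R-SAP, so the ranking does not choose between them. The SVC contrast in 6.5.3, "post*trtrnd*visit 2 0 0 -2 -1 0 0 1 -1 0 0 1 / cl divisor=2", has no tail option, so one-sided contrasts are not a general convention of the SAP. Survival has no code to compare.

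**The case against.** The strongest reply is that 6.5.1 states the only significance threshold in the plan. A contrast statement computes a quantity; it does not set an alpha. For harm to follow, a programmer must repair the effect name, keep the upper-tail option in spite of 6.5.1, and then compare that p-value with 0.05, which 6.5.1 does not allow. The solution table already supplies the two-tailed test, and the two p-values come from one t statistic. The SVC contrast also carries a stale name (post, absent from the 6.5.3 model), which suggests leftover template code rather than a decision to test one-sided. Finally, 6.5.2 refers to the MPRDR for the primary CAFS analysis, and 3.5 takes multiplicity handling from the M-SAP; neither was available for this review.

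Much of this stands. Two-tailed testing is the likely intent, Treat is probably a naming slip, and no error rate is breached if 6.5.1 is followed. But the SAP says the code specifies the analysis, and its revision history records that version 3.0 revised 6.5.2 to provide code for an adjusted analysis. Stale code elsewhere does not remove the tail conflict here. The MPRDR and M-SAP both rank below the R-SAP on this matter, so neither can override a contradiction inside it.

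**Conclusion.** The concern holds. The coded CAFS contrast cannot be run meaningfully as printed and, once the name is repaired, contradicts the two-tailed criterion at the first key secondary gate.

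The numerical consequence is conditional. It arises only if the one-sided p-value is judged against 0.05. It is then a doubling of benefit-direction error at one step, with no rise in that step's total size. The 87.6% power figure and the range for false CAFS claims (0.025%–2.0% rising to 0.05%–3.2%) rest on assumed inputs and show scale only. The point should be fixed, but it does not undermine the trial: it is an error in a test specification at a decision point, and it is cheap to remove.

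**What to change.** In SAP 6.5.2, replace the contrast with:

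`estimate 'Active vs. Placebo' trtrnd 1 -1 / cl;`

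With 0 declared as the reference level, placebo is ordered last, so these coefficients give active minus placebo. Add one sentence stating that the two-tailed p-value from this contrast is the one judged against 0.05 in the 6.5.1 sequence.

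The cost is one line of code and one sentence. It needs no new data, leaves the 6.5.1 criterion unchanged, and still allows a one-sided p-value to be reported descriptively. The stale effect name in the 6.5.3 contrast can be corrected at the same time.

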6.5.3 Repeated-measures Model

The specification of the repeated-measures linear mixed model and the primary linear contrast for estimating differences in 24-week change from baseline in a given continuous efficacy endpoint (ALSFRS-R total and domain scores, HHD upper extremity, lower extremity, and global average percentages, SVC, FVC by home spirometry, serum creatinine, serum NfL, urinary p75[ECD], ALSAQ-40 domain scores and SI, and CNS-BFS total score) are revised from those specified in the M-SAP to include a main effect of treatment and with the modification that treatment group is a three-level variable (i.e., placebo, 30 mg/d CNM-Au8, and 60 mg/d CNM-Au8).

The model will include fixed terms for discrete visit, treatment group (3 levels), treatment group \times visit interaction, centered time since symptom onset and centered time since symptom onset \times visit interaction, centered delta-FRS and centered delta-FRS \times visit interaction, centered baseline riluzole use and centered baseline riluzole \times visit interaction, and centered baseline edaravone

use and centered baseline edaravone \times visit interaction. The following equations describe the model with regimen random effects:

$$Y_{ij} = a_{k(i)} + \gamma_1 t_i + \gamma_{2,j} v_j + \boldsymbol{\gamma}'_3 \mathbf{z}_i + \gamma_{4,j} t_i v_j + \boldsymbol{\gamma}'_{5,j} \mathbf{z}_i v_j + \epsilon_{ij} \quad (\text{eqn. 1})$$

$$a_k \sim N(0, \sigma_r^2), \epsilon_{i \cdot} \sim N(\mathbf{0}, \mathbf{R}), \text{Cov}(b_{k(i)}, \epsilon_{ij}) = 0$$

where Y_{ij} is a given efficacy endpoint measured in participant i at visit j , $a_{k(i)}$ is a random intercept for regimen k to which participant i was assigned, v_j is an indicator variable for visit j , \mathbf{z}_i is the vector of covariates (centered time since onset, centered delta-FRS, centered baseline riluzole use, and centered baseline edaravone use) for participant i , t_i is an indicator variable for treatment t to which participant i was assigned, γ_1 , $\gamma_{2,j}$, $\boldsymbol{\gamma}_3$, $\gamma_{4,j}$, and $\boldsymbol{\gamma}_{5,j}$ are estimated parameters and vectors of parameters for the fixed effects, and ϵ_{ij} is the residual for participant i at visit j . The regimen-specific random effects are normally distributed with mean 0 and variance σ_r^2 . The vector of residuals for a given participant are normally distributed with mean $\mathbf{0}$ and an unstructured covariance matrix \mathbf{R} . The regimen-specific random effect for a given participant and residuals for that participant are uncorrelated.

The following SAS code specifies the model:

```
proc mixed data=xxx method=reml;
  class regimen id trtrnd visit;
  model Value = trtrnd|visit
            sx2b1|visit dFRS|visit rlz|visit edv|visit / solution cl;
  random intercept / subject=regimen type=vc;
  repeated visit / subject=id type=un;
```

where `id` is a participant study identifier, `trtrnd` is the randomly assigned treatment group, `visit` is the visit identifier, `Value` is value of the efficacy endpoint being tested for a given participant at a given visit, `sx2b1` is years since ALS symptom onset centered at the sample median, `dFRS` is pre-baseline slope centered at the sample median, `rlz` is an indicator of riluzole use at baseline, and `edv` is an indicator of edaravone use at baseline. The primary estimate will be the treatment-dependent difference in change from baseline to the Week 24 Visit. The estimate and its 95% Wald confidence bounds will be obtained by a linear contrast of adjusted means.

The estimand estimated by the primary linear contrast of the shared-baseline, repeated-measures linear mixed model is the mean difference in 24-week change from baseline of a given continuous efficacy endpoint in the two active treatment groups relative to the placebo group in the FAS population. The estimand is defined by the following attributes:

- Treatment: CNM-Au8 administered orally at dosages of 30 mg/d and 60 mg/d vs. placebo.
- Population: FAS population as defined in Section 6.1.
- Variables: absolute change in endpoint from baseline to the Week 24 Visit.
- Intercurrent event: treatment discontinuation: handled via treatment policy approach, all data will be used including data collected during the placebo-controlled period after treatment discontinuation. Missing data post-treatment, including data missing due to death, will not be imputed, handled via missing at random assumption.

- Population-level summary: difference in conditional means of active treatment relative to placebo.

Inference from this analysis is supportive of inference from the Bayesian shared-parameter, repeated-measures model for the primary endpoint and is the primary analysis for the secondary SVC endpoint.

The following SAS code specifies the linear contrast for an endpoint measured every 8 weeks and assuming that the sort order for treatment group is placebo, 30 mg/d CNM-Au8, and 60 mg/d CNM-Au8 and visits are sorted chronologically:

```
estimate "3|Act vs Plb|dWk 24"
          post*trtrnd*visit 2 0 0 -2 -1 0 0 1 -1 0 0 1 / cl divisor=2;
```

A significant difference in 24-week change in the direction of improved function would support inference that CNM-Au8 treatment reduced progression over 24 weeks for the efficacy endpoint being tested.

A separate supportive analysis for clinical endpoints (ALSFRS-R total and domain scores, HHD upper extremity, lower extremity, and global average percentages, SVC, FVC by home spirometry, ALSAQ-40 domain scores and SI, and CNS-BFS total score) will include centered baseline serum NfL level and the interaction of centered baseline serum NfL level and visit as additional covariates.

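### SAP 6.5.3: the SVC contrast is written on a term the model does not contain, and the model is still labelled shared-baseline; adjusting the SVC test for baseline SVC would be a cheap but possibly small gain

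*SAP*

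**What the plan says.** Section 6.5.1 makes the 6.5.3 repeated-measures model the basis of inference for SVC, after CAFS and before survival.

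The model code in 6.5.3 has these lines:
- CLASS: "class regimen id trtrnd visit"
- MODEL: "model Value = trtrnd|visit", continued by "sx2b1|visit dFRS|visit rlz|visit edv|visit / solution cl"
- RANDOM: "random intercept / subject=regimen type=vc"

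Residuals are unstructured over visits, and the baseline visit is one of the response rows. Baseline SVC is not a covariate.

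The text says the M-SAP model was revised "to include a main effect of treatment and with the modification that treatment group is a three-level variable". The version history entry for SAP 3.0 gives the reason: the shared-baseline assumption was dropped on FDA recommendation. The estimand paragraph of the current text nevertheless refers to the "primary linear contrast of the shared-baseline, repeated-measures linear mixed model".

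The target is stated plainly: "The primary estimate will be the treatment-dependent difference in change from baseline to the Week 24 Visit". For an endpoint measured every 8 weeks, the contrast that should deliver it is "post*trtrnd*visit 2 0 0 -2 -1 0 0 1 -1 0 0 1 / cl divisor=2".

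**The concern.** The contrast names an effect that the model does not contain. The SAS step would stop with an error, so this is a visible failure. What matters is how it is then repaired. One repair deletes `post*`. The other adds a `post` term, and the leftover shared-baseline label points that way. If the treatment main effect were removed at the same time, that repair would bring back the model the SAP says it gave up. This choice should be made in the SAP before data lock, not by a programmer.

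A second, smaller matter is precision. Each group has its own free baseline mean, so the tested quantity is Week 24 minus baseline in each group. Baseline SVC is scheduled for everyone but is not used to reduce the variance of that difference.

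**Working it through.** The documents give no SD, correlation, effect size or power for SVC, so there is no stated figure to reproduce.

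**1. Does the contrast fit the model?** The MODEL line generates `trtrnd`, `visit` and `trtrnd*visit`, and no effect containing `post`. SVC has four scheduled visits from baseline (0, 8, 16 and 24 weeks) and there are three groups, so `trtrnd*visit` has 12 columns, with visit varying fastest. Dividing the 12 coefficients by 2 gives:

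| Group | Wk 0 | Wk 8 | Wk 16 | Wk 24 |
|---|---|---|---|---|
| Placebo | 1 | 0 | 0 | -1 |
| 30 mg | -0.5 | 0 | 0 | 0.5 |
| 60 mg | -0.5 | 0 | 0 | 0.5 |

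Every row and column sums to 0, so no main-effect or covariate coefficients are needed. On `trtrnd*visit` the contrast is estimable and equals mean active change minus placebo change, which is the stated target. Now suppose `post` were added as a numeric 0/1 post-baseline indicator (an assumption, since it is undefined). The three baseline columns of `post*trtrnd*visit` would be all zero, while the contrast puts 1, -0.5 and -0.5 on them. It would not be estimable.

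**2. What would adjusting for baseline SVC gain?** Let rho be the baseline to Week 24 correlation and k the ratio of the Week 24 SD to the baseline SD, both after the existing covariates. Then

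Var(adjusted) / Var(change) = k²(1 - rho²) / (1 + k² - 2·rho·k).

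The denominator minus the numerator is (1 - rho·k)², so in large samples the factor never exceeds 1, and it equals 1 when rho·k = 1. At k = 1 it reduces to (1 + rho)/2.

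| k | rho 0.6 | rho 0.7 | rho 0.8 | rho 0.9 |
|---|---|---|---|---|
| 1.0 | 0.80 | 0.85 | 0.90 | 0.95 |
| 1.1 | 0.87 | 0.92 | 0.97 | 1.00 |
| 1.2 | 0.92 | 0.97 | 1.00 | 0.98 |
| 1.3 | 0.96 | 0.99 | 1.00 | 0.92 |

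Power for an effect that now has 80% is Φ(2.80/√factor - 1.96). At k = 1 this gives 88%, 86%, 84% and 82%. With 5 to 10% of participants assumed to have only a baseline SVC, the k = 1 range is 0.82 to 0.96.

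**3. What happens to the regimen term?** Assume 120 active participants, 40 placebo in each of four regimens and an SD of change of 15. The current SE is 15·√(1/120 + 1/160) = 1.81.

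- *Today.* The regimen intercept is constant over visits, so it cancels from Week 24 minus baseline. Cancellation is exact with complete data. With assumed dropout of 3 to 12% per visit, the largest weight left on any regimen intercept was 0.0015.
- *Baseline-adjusted, no regimen term.* The SE is 1.81·√factor = 1.62, 1.72 and 1.77 at rho 0.6, 0.8 and 0.9 (k = 1). A fraction 1 - rho of any regimen difference in SVC level now remains. It adds 0.75·[(1 - rho)·s]² to the variance, where s is the between-regimen SD of level and 0.75 = 0.75² + 3·0.25². For s = 2 and rho = 0.6 this is 0.75·0.64 = 0.48, on top of 1.62² = 2.62, and the two-sided error is 7.2%. At rho = 0.8 it is 5.5%. For s = 1 the errors are 5.5% and 5.1%.
- *Baseline-adjusted, regimen random intercept kept.* With no true regimen variation, simulation gives a mean SE of 1.75, 1.85 and 1.91 at rho 0.6, 0.8 and 0.9. Against 1.81 now, the gain survives only at the lower correlation.

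**The case against.** **The code slip is editorial.** The text of 6.5.3 makes the intended model clear, the coefficients are right, and the failure would be visible. All of this stands, and it limits the weight of the point. It does not remove the need to state the repair, because the leftover label supports a different one.

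**The change-score form was deliberate.** It follows a revision made on FDA recommendation and matches the stated variable. That also stands, so this part is an improvement to consider and not an error. A baseline covariate in a model for change does not force equal baseline means, so it does not reopen that decision. A reader might infer that the plan wastes baseline SVC. That goes too far: baseline stays in the likelihood and supports the missing-at-random handling. It is simply not adjusted for.

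**Baseline adjustment changes how regimens are handled.** This stands. Either some of any regimen difference in level stops cancelling, or a retained regimen intercept uses up the gain at high correlation.

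**A tempting stronger reading** is that, because the regimen intercept cancels, the SVC test has an inflated error rate when regimens differ in rate of SVC decline. The documents do not support that as a finding. They give no between-regimen spread in decline, so any error rate would be assumed. Participants are randomly assigned among regimens, and only concurrently enrolling regimens share controls (2.5, 6.1). Section 6.5.5 already plans a supportive SVC analysis with regimen random slopes, though it assumes linear change, and 6.5.13 compares controls across regimens. Section 6.5.11 refers further sensitivity analyses to the M-SAP, which was not supplied.

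**Conclusion.** Two statements in 6.5.3 are wrong as written: the contrast uses a term absent from the model, and the estimand paragraph keeps a label that the same section contradicts. Both conclusions rest on the text alone. The second conflict lies within the current section; the version history only explains it.

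The lack of adjustment for baseline SVC is a cheap opportunity of uncertain size: a variance factor of 0.80 to 0.95 under assumed equal SDs and correlation 0.6 to 0.9, and close to 1.00 under several plausible unequal-SD settings. It is worth doing only with an explicit decision on the regimen term.

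Nothing here shows that the planned SVC test is biased or has the wrong error rate. No change is requested for regimen differences in SVC decline. The practical reach is also limited, because SVC can be declared significant only after the primary analysis and CAFS succeed.

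**What to change.** 1. **Correct now.** In the ESTIMATE statement replace `post*trtrnd*visit` by `trtrnd*visit`, leaving the 12 coefficients and the divisor unchanged. Delete the shared-baseline label from the estimand paragraph. The cost is one line of code and one word.

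2. **Consider for the SVC test.** Model change at Weeks 8, 16 and 24 with the existing terms plus baseline SVC and baseline SVC by visit. The contrast becomes `trtrnd -2 1 1` with `trtrnd*visit 0 0 -2 0 0 1 0 0 1`, divisor 2.

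3. **If step 2 is adopted,** state whether a regimen term is kept and accept the consequence shown in the working. Leaving it out is a change from today's full cancellation. Carry the same form into the NfL-adjusted supportive model in 6.5.3 and the placebo multiple imputation in 6.5.10.

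Steps 2 and 3 need SAP wording and code only, with no new data. Participants with only a baseline SVC drop out of the change model. This deserves a sentence, because 6.5.3 says all data are used and SVC at Weeks 8 and 16 is done only when those visits are in clinic.
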